#### **11.5. Reporting Serious Adverse Events**

To ensure subject safety, every SAE occurring after the subject has provided informed consent, through the end of the study, regardless of causality, must be reported to Premier within 24 hours of learning of its occurrence. Drug-related SAEs reported to the study site after the EOS visit should also be reported to Premier.

Recurrent episodes, complications, or progression of the initial SAE must be reported as follow-up to the original episode, regardless of when the event occurs. This report must be submitted within 24 hours of the Investigator receiving the follow-up information. An SAE that is considered completely unrelated to a previously reported one should be reported separately as a new event.

In addition, SAEs (initial and follow-up) must be reported to Premier **within 24 hours of awareness** of the SAE or changes to an existing SAE. This should be done by emailing or faxing a signed copy of the **SAE Report Form** using the contact details below.

##### **Premier SAE Reporting Contact Details**

Email: [REDACTED]

Fax: [REDACTED]

Follow-up information provided should describe whether the event has resolved or continues, if and how it was treated, and whether the subject continued or withdrew from study participation.

If the SAE is not previously documented in the IB and is thought to be related to the investigational treatment, Magenta may urgently require further information from the Investigator for regulatory authority reporting. Magenta may need to issue an Investigator Notification to inform all Investigators involved in any study with the same investigational

treatment that this SAE has been reported. Each site is responsible for notifying their IRB/IEC of these SAEs in accordance with local regulations. Suspected unexpected serious adverse reactions (SUSARs) will be collected and reported to the regulatory authorities and relevant IRBs in accordance with local laws and regulations. It is the responsibility of the Investigator to notify the IRB of SAEs that occur at his or her site per IRB reporting requirements.

## **11.6. Overdose**

For this study, overdose is defined as a dose of study medication higher than the prescribed dose. In the case of overdose, the Investigator should be notified immediately, and supportive care given as indicated. Overdose will not be considered an SAE unless the overdose meets serious criteria as defined in [Section 11.2.4](#). In the event of an overdose, the Magenta Medical Monitor should be notified within 24 hours. The subject should be carefully monitored for potential adverse reactions and symptomatic treatment instituted as per standard of care.

## **11.7. Reporting Pregnancy**

Every pregnancy occurring up to 3 months after the last dose of study drug in subjects or partners of male subjects after the subject was administered MGTA-145, must be reported to Premier within 24 hours of learning of its occurrence. The pregnancy should be followed to determine outcome, including spontaneous or voluntary termination, details of the birth, and the presence or absence of any birth defects, congenital abnormalities, or maternal and/or newborn complications. A pregnancy occurring after signing the ICF and before the subject is enrolled will preclude study participation.

Pregnancy should be recorded on a Premier Pregnancy Data Collection Report Form and be reported by the Investigator to Premier using the contact information provided in [Section 11.5](#).

Pregnancy follow-up should be recorded on the same form and should include an assessment of the possible relationship to the study drugs of any pregnancy outcome. Any SAE experienced during pregnancy must be reported on the SAE Report Form.

If the father received study drug, consent to report information regarding pregnancy outcome needs to be obtained from the mother.

## 12. STATISTICS

A formal statistical analysis plan (SAP) will be developed that includes a detailed description of all planned analyses, pre specified exploratory analyses, and any data handling conventions.

### 12.1. Analysis Sets

Evaluable Analysis Sets: The evaluable analysis set for Part A will include all subjects that have received MGTA-145 and plerixafor and undergone successful apheresis collection. The evaluable analysis set for Part B will include all subjects that have received 2 consecutive doses of MGTA-145 and plerixafor, and successfully completed at least 1 of the 2 apheresis sessions.

The Safety Analysis Set: The safety analysis set will consist of all subjects who are enrolled and received a dose of MGTA-145. Subjects in this analysis set will be used for demographic, baseline characteristics, and safety summaries.

Pharmacokinetics Analysis Set: The PK analysis set will include all subjects with available MGTA-145 PK data and no major protocol deviations with relevant impact on PK data.

Pharmacodynamics Analysis Set: The PD analysis set will include all subjects with available PD data and no major protocol deviations with relevant impact on PD data.

In general, data will be presented for Parts A and B of the study separately.

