**Statistical Methods:**

A formal statistical analysis plan (SAP) will be developed and finalized prior to database lock. This document will provide further details regarding the definition of analyses, any data handling conventions, and analyses methodology to address all study objectives.

Statistical summaries will be descriptive in nature. All continuous variables will be summarized by dose cohort and visit (as applicable) using descriptive statistics (number of observations [n], mean, median, standard deviation [SD], minimum, and maximum). All categorical variables will be summarized by dose cohort and visit using frequency counts and percentages. Subjects who receive MGTA-145 will be included in the analyses. Data will be presented in aggregate and by cohort, if applicable. Subject baseline characteristics, including demographics and important disease characteristics, will be described using descriptive statistics.

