**Primary Endpoint; Part A:**

- The CD34+ cells/kg apheresis yield with 1 apheresis session after MGTA-145 + plerixafor dosing will be presented at each dose of MGTA-145 evaluated. A mean yield and 95% confidence interval (CI) will be presented.
- The number and percentage of subjects with administration-related toxicities and TEAEs will be summarized.

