#### 12.4.1. Statistical Methods and Analyses

Statistical summaries will be descriptive in nature. All continuous variables will be summarized by dose and visit (as applicable) using descriptive statistics (number of observations [n], mean, median, standard deviation [SD], minimum, and maximum). All categorical variables will be summarized by dose and visit using frequency counts and percentages. Estimated median, 25th and 75th percentiles and standard error of the mean (SEM) from Kaplan-Meier summaries will be presented for all time-to-event variables. Subjects will be grouped by dose in all analyses and results will be presented by Study Part where applicable. Any subject who receives MGTA-145 will be included in the analyses. No formal hypothesis testing will be performed.

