### **12.5. Sample Size Calculation**

There are no statistical hypotheses in this trial, therefore there is no sample size calculation. To address the objectives assessing proof of concept of mobilizing CD34+ cells after 1 or 2 days of dosing with MGTA-145 and plerixafor, a minimum sample size of 10 evaluable subjects is considered adequate.

Based on the safety profile including 79 subjects dosed with MGTA-145 in Phase 1 study 145-HV-101, 10 evaluable subjects are deemed a minimal number to assess common drug-related safety events.

The AE that is clearly related to MGTA-145 infusion is transient, Grade 1 back pain, which was observed in a majority of volunteers in the Phase 1 study 145-HV-101. With 10 evaluable subjects, there is sufficient subject exposure to assess for this AE.

Subjects enrolled in the study who are discontinued prior to receiving study drug may be replaced.

Additional subject(s) may be enrolled, if necessary, to ensure minimum numbers of evaluable subjects (i.e., subjects without any major protocol deviations affecting the primary endpoint). For the primary endpoint in Part A, 7 evaluable subjects are required; the first and second DMC assessments require 4 and 7 evaluable subjects, respectively. For the primary endpoint in Part B, 3 evaluable subjects are required.

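### Sections 12.1 and 12.5 of the protocol define an evaluable subject by different conditions, and under 12.1 inclusion turns on an undefined post-dose event close to the primary yield

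*Protocol*

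**What the plan says.** Section 12.1 defines the evaluable set separately for each part. For Part A: "The evaluable analysis set for Part A will include all subjects that have received MGTA-145 and plerixafor and undergone successful apheresis collection". For Part B a subject must have had both drugs on two consecutive days and "successfully completed at least 1 of the 2 apheresis sessions". Neither definition mentions protocol deviations, and the protocol does not say what makes a collection successful.

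Section 12.5 allows further enrolment "to ensure minimum numbers of evaluable subjects (i.e., subjects without any major protocol deviations affecting the primary endpoint"). Here the word rests on deviations alone, with nothing about doses received or cells collected. The same section attaches numbers to it: "For the primary endpoint in Part A, 7 evaluable subjects are required"; "the first and second DMC assessments require 4 and 7 evaluable subjects, respectively"; and 3 for the Part B primary endpoint. Section 8.1.1 also uses the word for the 4 subjects who make up the first cohort.

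Section 12.4.1 adds a general sentence, "Any subject who receives MGTA-145 will be included in the analyses", and the synopsis has its counterpart. In the synopsis, the Part A yield with 1 "apheresis session after MGTA-145 + plerixafor dosing will be presented at each dose of MGTA-145 evaluated", as a mean with a 95% CI. Table 6, footnote b, foresees a subject who is dosed but does not complete apheresis, and keeps that subject in follow-up.

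**The concern.** Neither definition contains the other and neither refers to the other, so two people following the text could count different subjects and report different primary means from the same data.

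This is more than a detail for the SAP. The synopsis has the SAP finalized before database lock, but the word acts while the trial is running. It decides when a cohort is full, when the DMC assessments have their 4 and 7 subjects, and whether another subject is enrolled. Those decisions will already have been made.

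For the estimate, the 12.1 condition is met or failed after dosing, and it lies close to the outcome. A subject whose collection fails or is cut short drops out of the set, and 12.5 then allows another to be enrolled to reach the minimum. If such subjects tend to collect less, the Part A mean describes those in whom collection worked rather than those who were dosed. The confidence interval does not show this.

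**Working it through.** **The plan's own figures.** The minimum is 7 (Part A) + 3 (Part B) = 10. The planned range follows from the two options for the second cohort: 4 + 3 + 3 = 10 and 4 + 7 + 3 = 14. Both agree with the protocol. There is no power calculation to reproduce.

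**The definitions side by side (Part A).**

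| Subject | Section 12.1 | Section 12.5 |
|---|---|---|
| Both drugs, collected, no major deviation | in | in |
| Both drugs, collected, major deviation affecting yield | in | out |
| Both drugs, no successful collection | out | in, unless the missing collection is itself classed as a major deviation |

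The second row is a firm mismatch. The third depends on a classification that the protocol does not give.

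**Effect on the Part A mean.** Let n be the number evaluable, with mean yield Y, and let one further dosed subject outside the set have yield rY. The all-dosed mean is Y(n + r)/(n + 1), so

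evaluable mean / all-dosed mean = (n + 1)/(n + r).

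The values n = 7 and n = 4 come from Section 12.5. The 4 applies because yield is reported by dose: if the second cohort moves to a reduced dose, the 0.03 mg/kg group stays at its first-cohort size. The values of r are assumptions.

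| r | n = 7 | n = 4 |
|---|---|---|
| 1 | 8/8 = 1.000 (0%) | 5/5 = 1.000 (0%) |
| 0.5 | 8/7.5 = 1.067 (6.7%) | 5/4.5 = 1.111 (11.1%) |
| 0 | 8/7 = 1.143 (14.3%) | 5/4 = 1.250 (25.0%) |

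**Comparison with sampling error.** The 95% CI half-width as a share of the mean is t(0.975, n − 1) × CV/√n. The protocol gives no SD, so the coefficient of variation (CV) is assumed.

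| CV | n = 7 | n = 4 |
|---|---|---|
| 0.3 | 28% | 48% |
| 0.5 | 46% | 80% |
| 0.7 | 65% | 111% |

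In units of Y, the zero-yield case moves the mean by 1 − 7/8 = 0.125 beside 7, and by 1 − 4/5 = 0.20 beside 4. Both are smaller than every half-width in their column.

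**Precision of an all-dosed mean.** Take 7 evaluable subjects with mean 1 and SD 0.5, and add one subject at r. With m = (7 + r)/8, SS = 6 × 0.25 + 7(1 − m)² + (r − m)², and the half-width is t(0.975, 7) × √(SS/7)/√8.

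- r = 0.5: m = 0.9375, half-width 0.41.
- r = 0: m = 0.875, half-width 0.49.

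The evaluable set alone gives 0.46.

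**The case against.** The two sections do different jobs. Section 12.1 defines analysis sets; the parenthesis in 12.5 governs top-up enrolment. They can be read as joint conditions: dosed, collected, and free of a major deviation affecting the endpoint. That reading is possible, but it is not stated, the wording in 12.5 is that of a definition, and the post-dose condition would remain. It is also fair that a missing collection might be classed as a major deviation, which would remove one of the two mismatches. The other would stand.

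Yield after dosing followed by apheresis is a defensible target for a collected-subject set, and the trial is descriptive, with no hypothesis and no yield threshold. That limits the harm to the reported estimate and its reproducibility. It also supports keeping the evaluable-set mean and adding to it, rather than replacing it.

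A reader might infer more than the protocol supports:

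- *That Section 12.4.1 is a third, competing rule.* It is a general sentence among descriptive methods. It cannot override the specific PK and PD sets, and by the same logic it gives way to the evaluable set, which 12.5 links to the primary endpoint.
- *That poor mobilizers are removed.* A poor mobilizer who completes collection stays in, unless success is judged by the amount collected, and the protocol does not say so.
- *That Part B is biased in a known direction.* Admitting one-session subjects lowers the two-day total. Leaving out subjects without a second dose, which Section 11 puts at the Investigator's discretion after a VOE, may raise it. The net direction is uncertain, and the question is separate from the conflict between 12.1 and 12.5.
- *That safety review is compromised.* The safety set in 12.1 includes every enrolled subject who received MGTA-145. Section 8.1.1 also says that the first-cohort subjects must complete treatment and the 1-week follow-up, which partly answers who counts toward the 4.

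**Conclusion.** The point holds as a conflict between two stated definitions of a word that has work to do during the trial. Followed as written, 12.1 selects the Part A yield set on an undefined post-dose event, and 12.5 permits enrolment to make up the number.

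The upward bias is conditional. It is absent if excluded subjects collected as much as the others, and reaches 14.3% (beside 7) or 25.0% (beside 4) if one excluded subject collected nothing. These figures rest on assumed yields, since the protocol gives no failure rate, and they lie within sampling error for a CV of 0.3 to 0.7. No size is claimed for the subject with a deviation, because the direction would depend on the deviation. No test or decision threshold on yield is affected. The wording should be corrected because one subject carries real weight in a study of 10 to 14, and the correction costs little.

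**What to change.** 1. Use one definition of evaluable in Sections 12.1 and 12.5, not dependent on the amount collected, and state which subjects count toward the 4 and 7 for the DMC assessments.
2. For Part A, keep the evaluable-set mean and CI. Beside it, present by dose the CD34+ cells/kg actually collected in all subjects who received both drugs. Count 0 when no product was obtained, including when apheresis was not started or was stopped because of an adverse event.
3. List collections not started for purely technical reasons, with the reason, and show the all-dosed mean with and without them.
4. Report the number dosed but not evaluable, and keep those subjects in the all-dosed summary when others are added under 12.5.
5. For Part B, only identify one-session subjects within the two-day total, and list the yield of dosed subjects outside the set.

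The cost is wording in 12.1 and 12.5 and one extra summary, with no additional subjects or procedures. The all-dosed mean may be lower than the evaluable-set mean, and its CI slightly narrower or wider, as the last calculation shows.

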**Figure 1: Part A (Single Dose) and Part B (Single Dose on 2 Consecutive Days)**

**Table 6: Schedule of Assessments: Part A (Single Dose)**

Study Period Procedures	Screening	Baseline	Mobilization /Apheresis	1-week follow-up (Day 7 to 10) b	End of Study (Day 30) b
	Day -30 to -2	Day -1	Day 1		
Informed consent	X				
Medical history	X	X			
Inclusion/exclusion criteria review	X				
Height		X			
Weight		X		X	
Physical examination	X	X		X	
Symptom-directed physical examination			X		
Vital signs a	X	X	X	X	
Serology c	X				
Serum or urine $\beta$ -hCG (females)	X	X			
12-lead ECG	X				
Urinalysis		X	X	X	
Chemistry d	X	X	X	X	
Hematology e	X	X	X	X	
Anti-drug antibodies		X		X	
Plerixafor administration			X		
MGTA-145 administration f			X		
Apheresis procedure			X		
Apheresis yield g			X		
PROMIS and ASCQ-Me questionnaires h			X	X	
Non-serious AEs and SAEs i	X	X	X	X	X j
Concomitant medications	X	X	X	X	X j

AE=adverse event; ASCQ-Me=Adult Sickle Cell Quality of Life Measurement Information; BPI=Brief Pain Inventory;  $\beta$ -hCG=beta-human chorionic gonadotropin; CFU= colony-forming unit; ECG=electrocardiogram; PK=pharmacokinetics; NRS=Numeric Rating Scale; SAE=serious adverse event

a Vital sign measurements will be taken in the sitting position after the subject has been resting for 5 minutes. Vital signs should be taken before any blood samples are drawn.

b If a subject does not complete dosing, there will not be follow-up visits. If a subject received MGTA-145 but did not complete apheresis, then follow-up visits are required.

c All subjects enrolled in Parts A will be screened for human immunodeficiency virus (HIV), hepatitis B surface antigen (HBsAg), human T-cell leukemia virus (HTLV), and hepatitis C virus (HCV) at the screening visit. Subjects who are HCV antibody positive must have a HCV ribonucleic acid (RNA) polymerase chain reaction (PCR) test.

d Clinical chemistry consists of sodium, potassium, chloride, bicarbonate, blood urea nitrogen, creatinine, glucose, calcium, aspartate aminotransferase (AST), alanine aminotransferase (ALT), alkaline phosphatase, albumin, total and indirect bilirubin. Clinical chemistry sample collection should be done prior to dosing on Day 1. All other clinical chemistry sample collections will be done on the morning of the assessment day.

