## 6.5. Treatment Assignment

This is an open-label study, in which all subjects will receive MGTA-145 and plerixafor as study drug.

All study subjects who are consented (including screen failures) will be assigned a subject identification number. The unique subject identification number will consist of 6 digits (xxxxxx).

The first 3 digits of the number will represent the study site and the second 3 digits will represent the subject at that study site. Any subject identification number that is assigned will not be reused even if a subject does not receive study drug.

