#### **9.5. MGTA-145 and Plerixafor Administration**

MGTA-145 should be diluted in 0.9% saline in accordance with the Study Pharmacy Manual. Dosing solutions of MGTA-145 prepared in 0.9% saline may be stored for no more than 8 hours at room temperature prior to administration. MGTA-145 is to be administered via a 3- to 10-minute IV infusion, approximately 2 hours after plerixafor SC injection. Instructions regarding administration are provided in the Study Pharmacy Manual.

Plerixafor is to be administered SC per the manufacturer's instructions.

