### **11.2. Adverse Events and Serious Adverse Events**

#### **11.2.1. Adverse Events**

Collection of non-serious AEs and serious adverse events (SAEs) will begin once the ICF is signed and continue until the EOS visit. Non-serious AEs and SAE reporting will end at the EOS visit. Any SAE occurring after the reporting period must be promptly reported if a causal relationship to study drugs is suspected.

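### The safety set requires a dose of MGTA-145, so a subject given only plerixafor, which is also study drug, is missing from every safety summary

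*Protocol*

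**What the plan says.** **Who is in the set.** Section 12.1 makes the safety analysis set "all subjects who are enrolled and received a dose of MGTA-145". On its use: "Subjects in this analysis set will be used for demographic, baseline characteristics, and safety summaries". Section 12.4.1 takes the same line for the analyses in general: "Any subject who receives MGTA-145 will be included in the analyses". The Statistical Methods part of the synopsis says the same.

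**What counts as study drug.** Section 6.5: "all subjects will receive MGTA-145 and plerixafor as study drug". Table 11, which describes the study drug, has a column for each product.

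**Order of dosing.** Section 9.5: "MGTA-145 is to be administered via a 3- to 10-minute IV infusion, approximately 2 hours after plerixafor SC injection".

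**Follow-up and data collection.**
- Table 6 footnote b (footnote c in Table 7): "If a subject does not complete dosing, there will not be follow-up visits". The same footnote keeps the visits for a subject who received MGTA-145 but did not complete apheresis.
- Section 11.2.1: "Collection of non-serious AEs and serious adverse events (SAEs) will begin once the ICF is signed and continue until the EOS visit".
- Section 11.4 limits collection for a subject who leaves study procedures early to safety data judged relevant to the MGTA-145 safety profile.
- Section 12.4.2 promises listings of all AEs, TEAEs and SAEs and names no analysis set for them.

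**The concern.** Exposure to study drug begins with the plerixafor injection, but membership of the safety set begins about 2 hours later. A subject who has an adverse event in between, and for whom MGTA-145 is then withheld, has been exposed to study drug and has stopped because of an event. That subject appears in no safety table, in either the numerator or the denominator.

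This touches a primary endpoint. In both parts, the primary safety endpoints include the incidence of TEAEs that lead to discontinuation of study drug. Part A gives one dose of each drug. Once the MGTA-145 infusion has started, only the rest of a 3- to 10-minute infusion can still be discontinued. The interval between the two drugs is therefore the main opportunity for a Part A subject to discontinue, and subjects who stop there are the ones the set leaves out. Section 11 itself describes vaso-occlusive events as associated with plerixafor use in this population, so an event after plerixafor is a realistic possibility.

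**Working it through.** No figure in the protocol depends on the definition of the safety set, so this is mainly a comparison of texts.

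**Step 1: who is in and who is out under Section 12.1.**

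| Course | MGTA-145 received? | In safety set? |
|---|---|---|
| Plerixafor, event in the gap, MGTA-145 then given | Yes | Yes |
| Part A: plerixafor, event, MGTA-145 withheld | No | No |
| Part B: stops in the Day 1 gap | No | No |
| Part B: dosed with both on Day 1, stops in the Day 2 gap | Yes (Day 1) | Yes |

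The exclusion is confined to subjects who never receive MGTA-145. No other set or provision in Section 12 brings them into a safety summary.

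**Step 2: where such an event would still be seen.**
- Section 11.2.1 collects AEs from consent to the end of the study.
- Section 11.5 requires SAE reporting whatever the causality.
- Section 12.4.2 lists all AEs.

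Two provisions work against this. The schedule footnotes remove the follow-up visits when dosing is not completed. Section 11.4 could keep a plerixafor-only event out of the database if it is judged not relevant to MGTA-145. The event is therefore lost from the summaries for certain, and only possibly from the listings.

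**Step 3: what one subject does to a percentage.** Suppose one plerixafor-only subject with an event is added to n MGTA-145 recipients without that event. The incidence changes from 0/n to 1/(n+1):
- n = 7 (Part A minimum, Section 12.5): 1/8 = 12.5%
- n = 10 (lower planned total): 1/11 = 9.1%
- n = 14 (upper planned total): 1/15 = 6.7%

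**Step 4: how likely such a subject is.** The protocol gives no rate of receiving plerixafor but not MGTA-145. For an assumed per-subject rate p, the chance of at least one among n subjects is 1 − (1 − p)^n:

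| n | p = 1% | 2% | 5% | 10% |
|---|---|---|---|---|
| 7 | 6.8% | 13.2% | 30.2% | 52.2% |
| 10 | 9.6% | 18.3% | 40.1% | 65.1% |
| 14 | 13.1% | 24.6% | 51.2% | 77.1% |

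The range of 6.8% to 77.1% is set by the assumed p and shows only that the protocol cannot settle the matter. It is also the chance of a plerixafor-only subject, not of a lost event.

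**Step 5: the stopping rules do not depend on this set.** At a true rate of 30%, P(X ≥ 3 of 4) = 4 × 0.3³ × 0.7 + 0.3⁴ = 0.0756 + 0.0081 = 8.37%, as in Table 9. P(X ≥ 4 of 7) = 12.60%, as in Table 10. Both are binomial counts in their own cohorts, over a window that Section 6.6.1 starts at MGTA-145 dosing. Section 12.1 does not enter.

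**The case against.** **The set fits the stated objective.** The primary safety objective in both parts names MGTA-145 only, and a subject never exposed to it says nothing about its own toxicity. This explains the definition, and a table restricted to MGTA-145 recipients should stay. It does not justify having no other table. What is tested is the combination, both components are study drug, and withholding MGTA-145 because of an event is itself informative.

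**The event is not lost.** In an open-label study of 10 to 14 subjects, an event in a listing or an SAE report is easy to see. This largely stands, and it keeps the point small. A listing still does not supply the incidence that the endpoint calls for.

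**Section 12.4.1 only says who is included.** It does not expressly exclude anyone. That is fair, but Section 12.1 is a full definition and does exclude.

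**A stronger reading that the protocol does not support.** A reader might infer that leaving out plerixafor-only events makes the combination look safer than the 30% plerixafor-alone VOE rate. With one lost event, for example, 3/8 (37.5%) would be shown as 2/7 (28.6%), on the other side of 30%. There are three reasons not to go that far:
- Section 6.6.1 words the 30% as events during and after apheresis, and Tables 9 and 10 concern subjects undergoing apheresis. A subject who stops in the gap never reaches apheresis, so such events are not shown to be part of the benchmark.
- The benchmark is applied through the DMC's counts from MGTA-145 dosing, which Section 12.1 does not govern. Neither 2 nor 3 events would meet the rule of more than 3 of 7.
- The study is descriptive with no hypothesis test, so crossing 30% in a summary table triggers nothing.

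**Conclusion.** The point holds as a gap in the completeness of safety reporting. By definition, a subject who receives plerixafor and never MGTA-145 is outside every safety summary, including a primary safety endpoint, although plerixafor is study drug. The gap applies only when MGTA-145 is withheld altogether.

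No size can be attached to it. How often it would happen is not in the protocol, and the percentages in the working rest on one hypothetical subject or on assumed rates. No bias against the VOE benchmark or in the stopping rules is shown. The priority is low, and the change is worth making because it costs almost nothing and one subject is visible at these sample sizes.

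**What to change.** 1. In Section 12.1, define the safety set as all enrolled subjects who received any dose of plerixafor or MGTA-145. Align Section 12.4.1 and the Statistical Methods part of the synopsis.
2. Present the safety summaries for MGTA-145 recipients (as now planned), for plerixafor-only subjects, and in total. The total is needed: a separate column alone would still leave these subjects out of any figure for the regimen as a whole.
3. Reconcile Table 6 footnote b, Table 7 footnote c and Section 11.4 with the AE collection to end of study in Section 11.2.1, so that it is clear what is collected, and how, for a subject who received plerixafor only. Which follow-up rule should apply is for the sponsor to decide.

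Cost: a few sentences and one or two table columns. The planned MGTA-145 summaries stay as they are, and the sample size is unaffected.
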